3.12 Interim Analyses

There are no interim analyses planned for this study.

4 STUDY ANALYSES

Unless otherwise specified, all summary tables described in this section will be presented for the Safety Population.

4.1 Subject Disposition

Subject disposition will include the number of subjects enrolled, included in the safety population and reasons for exclusion from the safety population, included in the bone metabolism population and reasons for exclusion from the bone metabolism population, completed all doses, not completed all doses with reasons, completed the study, discontinued study with primary reasons for not completing the study.

A by-subject data listing of study completion information, including the primary reasons for study withdrawal as recorded in the eCRF, will be presented.

4.2 Demographics and Baseline Characteristics

Demographic and baseline characteristics will be summarized. Age will be calculated as of the date of Informed Consent. Age, height, weight, body mass index (BMI), total hip T-score, total hip BMD, femoral neck T-score, femoral neck BMD, lumbar spine T-score, and lumbar spine BMD will be summarized using descriptive statistics (number of subjects, mean, SD, median, interquartile range, minimum and maximum). The number and percentage of subjects in each age, gender, ethnicity, race and total hip/lumbar spine/femoral neck T-score category (> -1.5 to < -1.0 ; > -2.0 to $<= -1.5$; > -2.5 to $<= -2.0$; > -3.0 to $<= -2.5$; and $<= -3.0$) will also be presented.

Medical history will be presented by MedDRA system organ class (SOC) and preferred term (PT) summarizing the proportion of subjects who have a condition noted.

All subject data collected for demographics and baseline characteristics will be presented in data listings.

4.3 Extent of Exposure and Compliance

Study drug exposure and compliance will be calculated using the data recorded on the Medication Dosing eCRF as follows:

- Duration of Exposure (days)
= date of last study medication – date of first study medication + 1
Note: If date of last dose is missing, the last dose recorded in the subject's diary will be used.
- Number of Doses Received
= number of successful applications from the subject dosing diary
- Compliance (%)
= (Number of doses received / Duration of exposure) x 100%

Descriptive statistics (number of subjects, mean, SD, median, interquartile range, minimum and maximum) will be used to summarize study drug exposure and compliance.

4.4 Concomitant Medication

Concomitant medications will be coded using the WHO Drug Dictionary. The number (and percentage) of subjects taking medications will be tabulated by Anatomical Therapeutic Chemical (ATC) class and preferred term (PT).

The tabulations will include concomitant medications taken from the date of the first dose of study medication (Day 1) until 1 week after the last dose of study medication. Medications that did not end prior to the first dose of study medication will be included in the summary.

Prior medications (those with start date prior to the first dose of study medication) will also be summarized by ATC and PT.

All recorded concomitant medications will be presented in a by-subject listing.

4.5 Analyses of the Primary Endpoint

The primary endpoint is the systemic exposure of the drug at Day 1, Day 15 and Day 29. Details are provided in the Pharmacometric Analysis Plan (PAP). Pharmacokinetic (PK) analyses will be conducted by Certara. Details of the planned PK analyses will be described in the PAP and provided as an Appendix to the CSR.

4.6 Analyses of Secondary Endpoints

4.6.1 Percent change of s-PINP from baseline to Day 15 and Day 29

The actual values, change from baseline values, percentage change from baseline values, geometric mean, geometric mean (SE) of ratio (post-baseline value to baseline value) in s-PINP will be summarized descriptively by visit, together with the 90% CI.

4.6.2 Change and percent change in serum calcium (albumin-corrected) from baseline to each post-dose timepoint

The actual values, change from baseline values, and the percentage change from baseline values will be summarized using descriptive statistics by visit and timepoint. A scatter plot will be used to present the relationship between the change from baseline (on y-axis) and total released dose as defined in Section 4.7.7 (on x-axis) for each timepoint.

4.6.3 Change and percent change in serum phosphorus from baseline to each post-dose timepoint

The same analyses described in Section 4.6.2 will be used.

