## 2.3. Secondary Endpoints

## 2.3.1. Pharmacodynamic (PD) Endpoints

- Percent change of s-PINP from baseline to Day 15 and Day 29.
- Change and percent change in serum calcium (albumin-corrected) from baseline to each post-dose timepoint.
- Change and percent change in serum phosphorus from baseline to each post-dose timepoint.
- Change and percent change in cAMP from baseline to each post-dose timepoint.

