Document AEs a concomitant med			After signing informed consent until follow up visit				
PK draw 				X	X	X	
Serum marker of metabolism (s-Pl	NP) 			X	X	X	
Drug supply / Dr		_		X	X		
Drug Accountab	ility				X	X	

- 1. A complete physical examination includes a review of the following systems: head/neck/thyroid, eyes/ears/nose/throat, respiratory, cardiovascular, lymph nodes, abdomen, skin, musculoskeletal, and neurological. Breast, anorectal, and genital examinations will be performed when medically indicated. After screening, any clinically significant abnormal findings from the symptom-directed physical examinations should be reported as AEs.
- 2. Including alcohol and tobacco use assessment.
- 3. Blood pressure, pulse rate, body temperature, and respiration rate are to be recorded predose at each study visit. Only blood pressure, pulse rate and respiration rate are to be recorded 1 hour after abaloparatide-sMTS application at each study visit during the treatment period. All blood pressure assessments will be orthostatic. Pulse rate will also be obtained at 15 minutes after abaloparatide-sMTS application at Day 1 (Visit 3), Day 15 (Visit 4) and Day 29 (Visit 5/EOT).
- 4. Height is to be measured at the screening visit/ Visit 1 in the standing position using a medical stadiometer.
- 5. During the Treatment Period, ECGs are to be performed predose after 5 minutes of rest and prior to any blood draw, and 1 hour after abaloparatide-sMTS application on Day 1 (Visit 3), Day 15 (Visit 4) and Day 29 (Visit 5/EOT).
- 6. All routine urinalysis will be performed on a sample freshly voided during the visit and sent to a local laboratory for microscopy if test is positive for micro-organisms via dipstick.
- 7. Blood draw for serum chemistry and hematology will be done during the Screening (Visit 1) and at predose on Day 1 (Visit 3), Day 15 (Visit 4) and Day 29 (Visit 5/EOT).
- 8. Blood draw for serum calcium, albumin and phosphorus will be done at predose and at 4 hours after abaloparatide-sMTS application on Day 1 (Visit 3), Day 15 (Visit 4) and Day 29 (Visit 5/EOT).
- 9. Blood draw for cAMP taken predose and at 30 minutes after abaloparatide-sMTS application on Day 1 (Visit 3), Day 15 (Visit 4) and Day 29 (Visit 5/EOT).
- 10. A 24 hour urine collection will start on Day -8 and complete on the day of the pre-treatment visit (Day -7).

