Serum calcium, phosphorus and albumin will be measured predose from the standard chemistry panel on Day 1, Day 15 and Day 29, and from a separate blood draw at 4 hours after abaloparatide-sMTS application on Day 1, Day 15, and Day 29. Blood draw for cAMP will be done predose and 30 minutes after sMTS application at Day 1, Day 15 and Day 29.

In the event of medically significant, unexplained, or abnormal clinical laboratory test values, the test(s) should be repeated and followed up until the results have returned to within the normal range or an adequate explanation for the abnormality is found. Clinically significant changes in laboratory tests that occur during the course of the study are to be reported as AEs unless included as part of a reported diagnosis (see Section 7).

The clinical laboratory will clearly mark all laboratory test values that are outside the normal range and the Investigator will indicate the clinical relevance of these out of range values.

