## 8.4. Description of Statistical Methods

## 8.4.1. General Approach

Baseline is defined as the last value obtained prior to the first dose of study medication.

For categorical data, summary tabulations of the number and percentage of subjects within each category of the parameter will be presented. For continuous data, the number of subjects, mean, median, standard deviation (SD), minimum, interquartile range (Q1 and Q3), and maximum will be presented, unless otherwise specified.

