3.4 Baseline Definitions

Unless otherwise specified, the baseline value is defined as the last value obtained prior to the first dose of study medication.

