4.6.4 Change and percent change in cAMP from baseline to each post-dose timepoint

The same analyses described in Section 4.6.2 will be used.

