4.7.7 Abaloparatide-sMTS Released Dose

A released dose is defined as “Initial Patch Content – Residual drug amount from Swab and Patch.” Descriptive statistics will be provided to summarize the released dose, the percentage of released dose to nominal dose, the percentage of release dose to initial patch content, the residual drug amount from the patch, the residual drug amount from the patch and swab, by visit. Released dose values that are negative will be set to 0 in the summaries, but the recorded values will be presented in the listings.

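### Day 15 and Day 29 changes in cAMP, calcium and phosphorus are referred only to the value before the first dose, so the acute response to that visit's patch is never summarised or plotted directly

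*SAP*

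**What the plan says.** SAP 3.4 states that, unless otherwise specified, "the baseline value is defined as the last value obtained prior to the first dose of study medication". Protocol 8.4.1 says the same: "Baseline is defined as the last value obtained prior to the first dose of study medication".

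SAP 4.6.2 (calcium) specifies no other reference. It plans actual values, change and percent change from baseline by visit and timepoint, and a scatter plot of the "relationship between the change from baseline (on y-axis) and total released dose as defined in Section 4.7.7 (on x-axis) for each timepoint". SAP 4.6.3 (phosphorus) and 4.6.4 (cAMP) adopt this by reference: "The same analyses described in Section 4.6.2 will be used". The protocol endpoint in 2.3.1 has the same form, for example "Change and percent change in cAMP from baseline to each post-dose timepoint".

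SAP 4.7.7 defines released dose for a patch as its initial content minus what is left on patch and swab. It summarises released dose and its components by visit, the last of them being "the residual drug amount from the patch and swab, by visit".

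Same-visit predose values are scheduled for all three markers:
- **cAMP:** Protocol Table 1, footnote 9: "Blood draw for cAMP taken predose and at 30 minutes after abaloparatide-sMTS application", on Days 1, 15 and 29.
- **Calcium, albumin, phosphorus:** Protocol 6.5.1: "Serum calcium, phosphorus and albumin will be measured predose from the standard chemistry panel on Day 1, Day 15 and Day 29", with a separate draw at 4 hours. Table 1, footnote 8 agrees. The Day 15 and Day 29 visit lists (6.2.7.2, 6.2.7.3) name only the 4-hour draw for these analytes, but the predose value comes from the chemistry panel, which both lists include.

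**The concern.** The 30-minute cAMP and the 4-hour calcium and phosphorus are acute responses to the patch just applied. On Days 15 and 29 the plan measures them from a value taken nominally 14 and 28 days earlier. Anything that moves the predose level in between enters the reported change. Subjects receive the drug daily and take calcium and vitamin D throughout (Protocol 4.4), so drift is possible, although the documents do not say how large it might be.

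The scatter plots are the SAP's only display relating released dose to a PD response. On Days 15 and 29 the x-axis describes one patch, while the y-axis describes that patch plus drift since Day 1. These visits follow home use, so they bear most directly on the primary objective of self-administration over 29 days judged by PK and PD markers.

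Two wording points add to this. SAP 4.7.7 does not define a *total* released dose, and 4.6.2 does not say whether visits are pooled in the plot.

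**Working it through.** **Inputs.** The baseline rule is from SAP 3.4 and Protocol 8.4.1, the sampling times from Protocol Table 1 (footnotes 8 and 9) and 6.5.1, and the planned outputs from SAP 4.6.2 to 4.6.4 and 4.7.7. There is no plan figure to reproduce. Neither document gives an SD or variance for these markers, so all variance ratios below are assumptions.

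**Step 1: what the planned change contains.** For Day 15 or 29,

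post − Day 1 predose = (post − same-visit predose) + (same-visit predose − Day 1 predose)

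That is acute change plus drift, and drift enters one for one. An acute rise of 1 unit is reported as 0, 0.5 or 1.5 when drift is −1, −0.5 or +0.5. On Day 1 drift is zero when the Day 1 predose sample is the baseline, so that visit is unaffected.

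**Step 2: what the planned tables still allow.** Actual values are tabulated by visit and timepoint, so a mean acute change can be had by subtracting means if the same subjects have both samples. Its SD cannot, because

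Var(post − pre) = Var(post) + Var(pre) − 2 Cov(post, pre)

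and the covariance is not tabulated. Nor do the tables give within-subject percent change or the per-subject relation to released dose.

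**Step 3: effect on the SD.** Let b be between-day variance, w within-day variance and r the variance of true response. Assume the day effect carries fully from predose to post-dose and is independent of the response.

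- Var(change from same-visit predose) = 2w + r
- Var(drift) = 2b + 2w
- The two share the same-visit predose error with opposite signs, so their covariance is −w
- Var(change from Day 1 predose) = (2w + r) + (2b + 2w) − 2w = 2w + 2b + r

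With q = b/w and s = r/(2w), the SD multiplier is √[(2w + 2b + r)/(2w + r)] = √[1 + q/(1 + s)].

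| q | s = 0 (equal true response) | s = 1 (response variance equals within-day noise of a change) |
|---|---|---|
| 0 | √1 = 1.00 | √1 = 1.00 |
| 0.25 | √1.25 = 1.12 | √1.125 = 1.06 |
| 0.5 | √1.5 = 1.22 | √1.25 = 1.12 |
| 1 | √2 = 1.41 | √1.5 = 1.22 |
| 2 | √3 = 1.73 | √2 = 1.41 |

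A simulation of 400,000 draws at s = 1/3 gave 1.00, 1.17, 1.33 and 1.58 for q = 0, 0.5, 1 and 2, against 1.00, 1.17, 1.32 and 1.58 by formula. This confirms the algebra, not the assumptions.

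**Step 4: effect on the scatter plot.** If released dose is unrelated to drift, its covariance with the change is the same under either reference, so the correlation is divided by the same factor. Take s = 1 and a correlation of 0.50 with the acute change:

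- q = 0: 0.50/1.00 = 0.50
- q = 0.5: 0.50/1.12 = 0.45
- q = 1: 0.50/1.22 = 0.41
- q = 2: 0.50/1.41 = 0.35

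**The case against.** The strongest reply is that nothing here is wrong. The SAP does what the protocol asks, the endpoints are secondary and descriptive, and no test or power is involved. Change from the untreated level is a legitimate quantity. The reference may also be deliberate: the protocol synopsis names change from predose for ECG heart rate but baseline for these markers. Delivery on the later visits is judged mainly by full PK profiles, a model-based comparison with Day 1, and released dose by visit. All of this stands, and it keeps the point small.

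The raw values are also not lost. SAP 3.10, 4.7.7 and 4.8.2 put the laboratory and released-dose data in listings, and with about 22 subjects someone could rebuild the acute changes by hand. Protocol 8.4.11 allows post-hoc exploratory work. But a listing is not a planned analysis, and choosing the reference value after seeing the data is weaker than stating it now.

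The magnitude is conditional, and this objection holds. At q = 0 there is no loss. If true response is smaller when the predose level is higher, a negative covariance c between response and that day's level adds 2c to the variance of the change from baseline. The inflation then shrinks, and it reverses if c is below −b.

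On terminology, *total* may simply mean patch and swab residuals together. Residual drug is measured only for the three clinic patches, so a 29-day cumulative dose is not available. This part is a wording note and would not merit comment alone.

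**Conclusion.** The point holds as a suggestion worth considering. For all three markers on Days 15 and 29, the only planned change combines acute response with predose drift, and it is plotted against the released dose of one patch. The samples that would separate the two are already scheduled. The SAP and protocol agree with each other, Day 1 is unaffected, and PK remains the main evidence of delivery.

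That drift enters one for one is an identity and rests on no assumption. The SD multipliers (1.00 to 1.73) and the fall in correlation (0.50 to as low as 0.35) rest on assumed variance ratios, an additive day effect that carries over to the post-dose sample, and released dose unrelated to drift. They show what could happen, not what this trial will show.

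**What to change.** Add to SAP 4.6.2, 4.6.3 and 4.6.4:

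> Change and percent change from the same-visit predose value to the 30-minute value (cAMP) or the 4-hour value (albumin-corrected calcium, phosphorus) will be summarised for Days 1, 15 and 29. A scatter plot of this change (y-axis) against the released dose of the patch applied at that visit (x-axis) will be presented by visit.

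Keep the change-from-baseline summary and plot, since they are the protocol-worded analysis. In 4.6.2, use the term that 4.7.7 defines and state whether visits are pooled.

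This extends a rule the SAP already has: 4.8.3.2 and 4.8.4 specify change from pre-dose by visit for pulse and ECG. The cost is SAP wording, one extra set of summary rows and one extra plot per marker. No sample is added and no planned output is removed.

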4.6.4 Change and percent change in cAMP from baseline to each post-dose timepoint

The same analyses described in Section 4.6.2 will be used.

4.7 Analyses of Other Endpoints

4.7.1 Subject satisfaction and convenience of treatment as measured by Treatment Satisfaction Questionnaire for Medication (TSQM-9) at Day 15 and Day 29

Subject satisfaction and convenience domain scores will be calculated following the descriptions in section 3.3 of TSQM user manual version 1.1 (October 2018).

Descriptive statistics (number of subjects, mean, standard error [SE], median, interquartile range, minimum and maximum) will be used to summarize TSQM-9 satisfaction and convenience domain scores and will be tabulated for Day 15 and Day 29.

Adherence will be measured by s-PINP. The median percent change from baseline in s-PINP will be obtained at Day 15 and at Day 29.

Descriptive statistics for each of TSQM-9 satisfaction and convenience domain scores will be presented for subject by adherence (i.e., \geq or $<$ the median percent change from baseline in s-PINP) at Day 15 and Day 29, respectively.

4.7.2 Subject acceptability measurement (5-point Likert Scale) at Day 1, Day 15 and Day 29

Subject acceptability measurement is based upon a 5-point Likert-like scale from 1 (least acceptable/negative experience) to 5 (most acceptable/positive experience). Subject acceptability measurement at each visit and changes from baseline will be summarized with descriptive statistics (number of subjects, mean, standard error [SE], median, interquartile range, minimum and maximum).

Descriptive statistics for the baseline and the change from baseline will be presented for subject with adherence (as defined in Section 4.7.1) vs. without adherence at Day 15 and Day 29, respectively.

4.7.3 Subject preference for treatment attributes at Day 1, Day 15 and Day 29

Since the data is collected as free-text field in eCRF, data will be classified after database lock for summary and further analyses. Association between subject preference for treatment attributes and subsequent acceptability and satisfaction will be evaluated separately for: outcome (effectiveness/safety) and other attributes (duration, frequency of use, mode of intake).

4.7.4 Investigator assessment of signs of local skin reaction using a 4-point scale at Day 1, Day 15 and Day 29

For each sign, the number (%) of subjects in each response category (none, mild, moderate, and severe) will be provided per visit and timepoint. The maximum severity of each sign of local skin reaction will be similarly summarized with the number (%) for each response category by visit and by timepoint, respectively. Aggregate summary of occurrence for each sign of local skin reaction will be similarly summarized with the number (%) for each response category by timepoint.

4.7.5 Subject assessment of symptoms of local skin reaction using a 4-point scale from Day 1 through Day 29 as recorded in the subject diary

For each symptom, descriptive statistics (number of subjects, mean, SD, median, interquartile range, minimum and maximum) will be used to summarize 4-point scale scores (0=None,

1=Mild, 2=Moderate,3=Severe) collected during the treatment period by timepoint. The maximum severity of each symptom of local skin reaction per subject during the treatment period will be summarized with the number (%) for each response category by visit and by timepoint (including any post dose timepoint), respectively.

In addition, for each symptom, the number (%) of subjects in each response category (none, mild, moderate, and severe) at clinic visits (Day 1, Day 15 and Day 29) will be provided per visit and timepoint. The maximum severity of reaction scores at clinic visits will be similarly summarized for each response category by visit and by timepoint, respectively.

For each symptom, the number (%) of subjects in each response category (none, mild, moderate, and severe) at Day 36 follow-up will be provided for each telephone contact, in clinic visit and overall (telephone contact + in clinic visit) group category.

Aggregate summary of occurrence for each symptom of local skin reaction will be similarly summarized with the number (%) of subjects in each response category by timepoint.

All application site local tolerability assessment scores will be presented in a listing.

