## 5.6. Treatment Compliance

To ensure treatment compliance, the Investigator or designee will supervise all study drug administration that occurs at the site. At each study visit, the Investigator or designee will review subject compliance with study drug administration and will remind the subject of study drug dosing requirements.

Subject compliance will be ascertained by using the data entered on the subject diaries as well as the total used and unused abaloparatide-sMTS returned at each study visit.

Discrepancies will be discussed with the subjects, documented in the medical charts, and recorded in the eCRF as appropriate. If a subject does not take the required medication or supplements (abaloparatide-sMTS, calcium and vitamin D), the reason for the missed dose is to be recorded by the subject in the subject diary.

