## **Subject Reported Outcomes:**

- TSQM9- Global Satisfaction and Convenience Domains
  - Mean TSQM-9 score (±standard error [SE]) for each domain will be tabulated for Day 15 and Day 29 for the subjects who completed the study
  - Association between improvement in convenience and satisfaction score (TSQM9) and adherence (definition of adherence will be provided in the SAP)
- 5-point Likert-like scale of acceptability will be tabulated and summarized
  - Mean score ( $\pm$ SE) will be tabulated for Day 1, 15, and 29
  - Association between improvement in acceptability and adherence will be assessed
- Subject Preference for treatment attributes will be summarized
  - Pending data availability, association between subject preference for treatment attributes and subsequent acceptability and satisfaction will be evaluated separately for: outcome (effectiveness/safety) and other attributes (duration, frequency of use, mode of intake).

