2 SUBJECT ANALYSIS POPULATIONS

2.1 Population Definitions

Three subject populations will be considered in the statistical analyses of this study.

Safety Population

The Safety Population is defined as all subjects who received at least 1 dose of study medication.

Pharmacokinetic Analysis Population

The PK Analysis Population will include all subjects in the Safety Population who have sufficient evaluable plasma concentrations to reliably estimate one or more PK parameters. Further details will be provided in the Pharmacometric Analysis Plan (PAP).

Bone Metabolism Population

The Bone Metabolism Population is defined as all subjects in the Safety population who have baseline and at least one post-baseline s-PINP.

The primary population for all safety analyses will be the Safety Population, and the primary population for PK analyses will be the Pharmacokinetic Analysis Population. The primary population for the analysis of the secondary endpoints (i.e., pharmacodynamic and other endpoints) will be the Safety Population, unless otherwise specified. The Bone Metabolism Population will be used for all analyses involving s-PINP.

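### SAP 4.7.1 and 4.7.2 define adherence by a within-sample median split of s-PINP change, so about half the subjects are labelled as without adherence whatever their dosing

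*SAP*

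**What the plan says.** Protocol 8.4.3 (Subject Reported Outcomes) plans two associations: "Association between improvement in convenience and satisfaction score (TSQM9) and adherence (definition of adherence will be provided in the SAP" and "Association between improvement in acceptability and adherence will be assessed". The secondary objective in the protocol synopsis lists adherence to therapy among the usability measures.

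SAP 4.7.1 supplies the definition: "Adherence will be measured by s-PINP. The median percent change from baseline in s-PINP will be obtained at Day 15 and at Day 29". TSQM-9 satisfaction and convenience scores are then described for subjects at or above that median and for those below it, at each of the two visits. SAP 4.7.2 takes over the same split for acceptability, with results "presented for subject with adherence (as defined in Section 4.7.1) vs. without adherence at Day 15 and Day 29". On the population, SAP 2.1 states: "The Bone Metabolism Population will be used for all analyses involving s-PINP".

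The SAP also holds a separate dosing measure. SAP 4.3 takes doses received as the "number of successful applications from the subject dosing diary" and derives compliance as ("Number of doses received / Duration of exposure) x 100"). Protocol 5.6 bases compliance on the diary and on counts of returned used and unused patches. Neither measure is linked to TSQM-9 or acceptability in any planned table. SAP 5 lists only the added Bone Metabolism Population as a change from the protocol.

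**The concern.** A cut at the sample's own median fixes the size of the two groups before any data are seen. The share labelled as without adherence therefore says nothing about how many patches were applied. It will be about half in a perfectly compliant study and about half in a poorly compliant one.

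The same report could show a subject with 100% compliance under SAP 4.3 and place her in the group without adherence under SAP 4.7.2. She could also change group between Day 15 and Day 29 with no change in dosing, because the median is taken afresh at each visit. A low s-PINP rise can come from biology, delivery or assay variation as well as from missed doses.

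At stake is the reading of the two planned associations: the acceptability table would look like a finding about adherence when it is a breakdown by relative PD response.

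A related gap sits in the same section. The protocol speaks of improvement in TSQM-9, but SAP 4.7.1 tabulates only the scores at each visit by group.

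**Working it through.** The documents give no figure for the size of the adherence groups, so there is nothing to reproduce. The check applies the SAP rule directly.

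**Inputs.** About 22 subjects enrolled and at least 18 completing (protocol synopsis, number of subjects). The split is at or above versus below the sample median (SAP 4.7.1). Here n is the number with s-PINP at the visit; a subject without a value falls in neither group.

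**1. Size of the lower group, no ties.** For even n the median lies between the two middle values, so n/2 subjects are below it. For odd n the middle subject equals the median and goes to the upper group, so (n − 1)/2 are below. Both equal floor(n/2).

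| n | below the median | share |
|---|---|---|
| 18 | 9 | 50.0% |
| 19 | 9 | 47.4% |
| 20 | 10 | 50.0% |
| 21 | 10 | 47.6% |
| 22 | 11 | 50.0% |

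Simulation gave the same counts in every sample. With n = 22 the lower group had 11 subjects whether everyone was given full, half or no compliance, because a common shift leaves the ranks unchanged.

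**2. Ties.** Ties at the median can only lower the count. With an assumed mean change of 40% and SD of 30%, the count was exactly floor(n/2) in about 99% of samples when values were rounded to one decimal (n = 18 and 22), and in 87% to 89% when rounded to whole percents.

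**3. Fully dosed subjects in the lower group.** Take the case most favourable to the SAP rule: k subjects miss applications and all k rank lowest on s-PINP. Then floor(n/2) − k fully dosed subjects are still in the lower group. For n = 20 and assumed k = 0, 1, 2, 4 that is 10, 9, 8 and 6 of 10. For k = 2 it is 7/9 = 77.8% at n = 18 and 9/11 = 81.8% at n = 22. A less ideal case, with 2 of 22 subjects receiving no drug effect and an assumed effect of 1 or 2 SD in the rest, puts on average 9.4 or 9.1 fully dosed subjects in the lower group, together with 1.6 or 1.9 of the 2.

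**4. Changing group between visits.** Suppose all are fully compliant and the Day 15 and Day 29 changes are bivariate normal. For assumed correlations of 0.5, 0.7 and 0.9, about 34%, 26% and 15% of subjects change group. The large-sample value, arccos(ρ)/π, is 33.3%, 25.3% and 14.4%.

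**5. The dosing scale for contrast.** If every subject applies all 29 patches, each has 29/29 = 100% under SAP 4.3 and nobody is low. One missed dose between first and last gives 28/29 = 96.6%. On this scale the picture depends on dosing.

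**The case against.** The strongest reply is that the protocol hands the definition to the SAP, the SAP gives one openly, and the primary objective itself judges self-administration on PK and PD markers. A PD marker as a proxy for adherence is then no departure. The protocol asks for an association, not an adherence rate, and a median split of any continuous variable fixes the group sizes yet can still show an association. All of this stands.

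It rules out three stronger readings that a reader might draw.

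- *The protocol's planned analysis is not delivered.* Tables by adherence, as the SAP defines it, are planned, and SAP 4.7.2 does tabulate change in acceptability by group. If s-PINP tracks dosing, these tables carry some of that information.
- *The split can be right only if exactly floor(n/2) subjects miss applications.* That holds only if adherence is a yes/no matter of zero misses. On a graded view, ranking by a marker that follows dosing can be informative.
- *s-PINP is an invalid marker of adherence.* The documents do not show this.

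It is also fair that a diary count is self-reported and may sit near its ceiling, that k, the correlations and the drug effects above are assumptions, and that scores by visit are an understandable reading of TSQM-9 improvement, given that the questionnaire is first completed on Day 15.

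What the reply does not answer is the label. Freedom to define adherence does not make a fixed half of the sample non-adherent, and the dosing data are left unused for this question.

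**Conclusion.** The point holds, as a minor one. Barring ties, 9 to 11 of 18 to 22 subjects will be labelled as without adherence at each visit regardless of dosing. This needs no assumption about the s-PINP distribution or the drug effect; with ties it is an upper bound. The shares of fully dosed subjects in the lower group and of subjects changing group are illustrations that rest on the stated assumptions.

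No explicit protocol definition is broken. The defect is that the tables show satisfaction and acceptability by relative s-PINP response under the name of adherence, while no planned output relates them to dosing. The reach is limited to descriptive tables of other endpoints with no tests. The primary PK endpoint and the SAP 4.3 compliance summary are unaffected.

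**What to change.** 1. **Relabel.** In SAP 4.7.1 and 4.7.2, name the groups at or above / below the median s-PINP percent change (PD response), and remove the adherence wording. Nothing planned is lost.

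2. **Add a dosing display.** Show change in acceptability from Day 1, and TSQM-9 domain scores at Day 15 and Day 29, against dosing adherence kept continuous: successful applications up to the visit divided by planned dosing days up to the visit, checked against the patch returns in protocol 5.6. A scatter plot, already used in SAP 4.6.2, or a rank correlation is enough. State the denominator for visits within the ±2-day window and for early end-of-treatment visits, and note that a failed attempt that is not repeated lowers the figure.

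   State also that this measure is visit-specific and differs from the whole-period compliance of SAP 4.3. At Day 15 the denominator differs for everyone who continues past Day 15: one dose missed before then gives 14/15 = 93.3% against 28/29 = 96.6%. At Day 29 it differs for subjects whose last dose came before the visit: stopping after 10 doses without a miss gives 10/29 = 34.5% of the 29 planned days against 10/10 = 100%. It should not be described as differing only for early stoppers.

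3. **Record the reading of improvement.** State in SAP 5 that TSQM-9 has no score before Day 15, so improvement can only be the change from Day 15 to Day 29, and show that change.

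**Cost.** SAP wording and a few extra outputs; all data are already collected. The downside is limited variation. Protocol 5.6 says that "the Investigator or designee will supervise all study drug administration that occurs at the site", which leaves 29 − 3 = 26 home doses to Day 29 and 15 − 2 = 13 to Day 15. At assumed independent miss rates m of 2%, 5% and 10%, (1 − m)^26 = 59%, 26% and 6.5% of subjects would tie at 29 of 29, and (1 − m)^13 = 77%, 51% and 25% at 15 of 15. Near-ceiling adherence would itself be worth reporting. With 18 to 22 subjects the display stays descriptive.
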